13.4 Analysis Plan

13.4.1 Analysis Populations.

For the primary outcome and each secondary outcome, the analysis population will consist of all individuals with a measurement for that outcome, in an intent-to-treat framework.

13.4.2 Primary Analysis of Primary Endpoint(s)/Outcome(s)

The primary endpoint is a continuous measurement. All individuals whose primary endpoint is measured will be included in the analysis population.

For the comparison of immunoreduction vs no immunoreduction, we will reject the null hypothesis if the two-sided rank-sum p value comparing the -fold increase between the two groups falls below 0.05.

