This study will investigate the effect of an additional dose of either the Moderna or Pfizer-BioNTech COVID-19 vaccine, with or without a reduction in immunosuppression, in participants who demonstrate a negative or low (≤ 2500 U/mL) anti-RBD titer after a completed mRNA COVID-19 vaccine series. Response will be assessed using the Roche Elecsys® anti-SARS-CoV-2 S assay which has an approximate 1:1 conversion to World Health Organization binding antibody units (BAU). Anti-S1/RBD levels are well correlated with neutralizing antibody against SARS-CoV-2 and with vaccine sero-protection in the general population.^{37,38} The precise cutoff that connotes protection from infection is not established for immunocompromised persons. Early studies, however, indicated anti-S1/RBD levels of 15-144 BAU⁴⁰ are correlated with live virus neutralization of ancestral variants in convalescent persons. Subsequent analyses of vaccine efficacy across trials indicated a level 2-4-fold higher for vaccine-evoked neutralization (compared to convalescents) best correlates with vaccine efficacy.⁴¹ Consistent with this, several studies in transplant recipients have suggested anti-S1/RBD levels of 100-250 BAU after vaccination as associated with in vitro neutralization; below this level, neutralizing capacity against SARS-CoV-2 variants is not reliable and suggests higher risk of infection. Notably, variants of concern, particularly the Omicron variant and its sublineages demonstrate significant immune evasion and need for 10-20-fold higher levels of antibody to neutralize than required for ancestral variants.⁵²⁻⁵⁵ Version 6.0 of the protocol increases the SARS-CoV-2 S titer for eligibility from 250 U/mL to 2500 U/mL to account for the findings that suggest the antibody levels needed to neutralize Omicron are significantly higher.⁵⁸

Rationale for Selection of Investigational Product or Intervention

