In observational series focusing on those with negative antibody levels after a two-dose mRNA series, seroconversion rates were 27-44%, generally to lower titers. Additionally, preliminary data from Johns Hopkins indicate that fully one third of SOT recipients who receive a third vaccine dose continue to demonstrate zero neutralizing antibody versus the delta variant.⁴⁷ In contrast, among those with low, but detectable antibody after a two-dose series, seroconversion rates above threshold were 80-100% and to a level approximately 5-fold higher than that observed in seronegative participants.⁴²⁻⁴⁵ Notably, one cohort series of patients on maintenance belatacept therapy showed poor seroconversion rates after a third mRNA dose (increasing from 6% to 37%), noting a 5% clinical COVID-19 breakthrough rate with 50% mortality.

In the randomized trial of a third dose of Moderna vaccine given to 60 SOT recipients (20 kidney recipients), irrespective of anti-RBD antibody level, median fold-change in anti-RBD antibody level of approximately 40x in the vaccination group, and 75x higher than seen in the placebo group (median post intervention level 314 vs 1.2 u/mL). Additionally, surrogate plasma neutralization capacity versus “wildtype”/vaccine strain SARS-CoV-2 increased from 37% at baseline to 60% after a third dose. SARS-CoV-2-specific, polyfunctional CD4 and CD8 T cell responses were assessed via intracellular cytokine staining (IFN-γ and IL-2) in a subset of patients demonstrating higher median counts (432 vs 67 cells/10⁶ CD4+ T cells).⁴⁵ In this trial, however, <20% of participants had any neutralizing capacity versus the Omicron variant following a third dose. This emphasizes the need to increase peak binding antibody responses in vulnerable transplant recipients, including those with low-level, positive antibody after standard vaccination series, in an effort to reduce the risk period for infection during expected antibody wane.^{56,57}

Reassuringly, in these collective series with limited follow up, reactogenicity was similar after a third dose as that described in two-dose mRNA series, with no serious or medically-attended adverse events reported.

One case of mild rejection was noted in a heart transplant recipient after a third dose of Pfizer-BioNTech vaccine (negative DSA), uncertain if related to vaccination.⁴²⁻⁴⁶

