6.7 Immunosuppression Reduction

6.7.1 Immunosuppression (IS) Reduction

Participants on a tacrolimus-based regimen that includes MMF (or equivalent), with or without corticosteroid:

MMF (or equivalent) will be withheld for five days prior to and 2 weeks following vaccine administration. During the interval that MMF is withheld, no adjustments will be made to the CNI or corticosteroid dose.

Participants on a tacrolimus based regimen with a trough level ≥ 5 ng/mL, with or without ≤ 5 mg Prednisone (or equivalent) and no MMF or other antimetabolite

Reduce CNI by 25% of starting dose for 5 days prior to and 2 weeks following vaccine administration.

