13.3 Measures to Minimize Bias

All participants will be randomized to receive immunoreduction or no immunoreduction prior to receipt of the vaccine. Randomization will be clustered by study site, and stratified by pre-dose titer (<50 vs ≥50 U/mL). Treatment group assignment will be unmasked to participants and clinical study staff. All laboratory staff will be masked to treatment assignment.

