13.7 Sample Size Considerations

Comparison of the primary endpoint will use a two-sided ranksum test. There will be 400 patients, 200 per treatment group. Power calculations assume an α of 0.05. The power of the study will depend on the distribution of -fold changes in each group.

We ran simulations in which -fold changes are log-normally distributed, and computed power based on the ratio of -fold change between the two groups. For example, if the average -fold increase in one group is a twofold increase and in the other group, a threefold increase, the ratio of -fold change is $3/2$ or 1.5. (This does not mean that each individual in one group experienced a twofold increase; some individuals would experience a greater increase, and some a smaller increase.) In the simulation, with an N of 400, generally the study has 80% power to detect a difference of 20% (e.g. mean 2.5-fold increase in one group vs 3-fold increase in the other.)

14. Identification and Access to Source Data**14.1 Source Data**

Source documents and source data are the original documentation where subject information, visits consultations, examinations and other information are recorded. Documentation of source data is necessary for the reconstruction, evaluation and validation of clinical findings, observations, and other activities during a clinical trial.

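### The primary rank-sum test leaves out the randomisation titre stratum and any adjustment for baseline titre, and no effect estimate or interval is planned for the primary endpoint

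*Combined protocol and SAP*

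**What the plan says.** - **Test.** Section 13.4.2: "we will reject the null hypothesis if the two-sided rank-sum p value comparing the -fold increase between the two groups falls below 0.05". Section 13.7 confirms the choice: "Comparison of the primary endpoint will use a two-sided ranksum test".
- **Randomisation.** Section 13.3: "Randomization will be clustered by study site, and stratified by pre-dose titer (<50 vs ≥50 U/mL". Neither site nor titre stratum appears in section 13.4.2. Appendix 1 randomises the individual participant once eligibility is complete.
- **Baseline titre.** It enters as the denominator of the fold increase (3.2), with values under 10 U/mL set to 10 (13.2).
- **Estimates.** The only confidence interval in section 13.4 is for severe adverse events (13.4.3). The synopsis lists log titre at 30 days as a secondary endpoint, but section 13.4.3 gives no method for a continuous outcome.
- **Eligibility range.** Section 1.1 records that version 6.0 "increases the SARS-CoV-2 S titer for eligibility from 250 U/mL to 2500 U/mL".
- **Regimen.** Under section 6.7.1 the reduction arm either withholds MMF or follows a second rule, "Reduce CNI by 25% of starting dose for 5 days prior to and 2 weeks following vaccine administration", according to baseline regimen. Section 2.5 asks whether response is associated with regimen. The stratified repeats in section 13.4.4 cover only dose timing and vaccine brand, and section 13.4.5 leaves other associations to exploration without a method.

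**The concern.** A trial that stratifies its randomisation by a factor thought to be prognostic should carry that factor into the analysis. Stratification forces the arms to be alike on titre, so the true variability of the treatment comparison shrinks. An unadjusted test still measures its result against the full, unstratified variability. If the factor matters, the test rejects too rarely under the null and gives up power.

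Dividing by baseline is not the same as adjusting for it. A fold increase fixes the slope of log Day 30 titre on log baseline at exactly 1, and any other slope leaves explainable variance in the comparison.

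The missing estimate is a separate matter and needs no assumptions. The hypothesis (2.1) is a higher fold increase without more alloimmune events, and section 13.5.1 speaks of weighing risk against benefit. A p value gives no size of benefit to weigh. Section 13.7 reasons in ratios of fold change, yet the plan never commits to estimating that ratio.

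**Working it through.** **1. The stated power.** Inputs from section 13.7: "There will be 400 patients, 200 per treatment group"; "Power calculations assume an α of 0.05"; log-normal fold changes; ratio 1.2; power 80%. No SD is given, so I solve for it, using the rank-sum's efficiency of 3/π under normality:

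SD = ln(1.2) × √(3/π) ÷ [(1.960 + 0.842) × √(2/200)] = 0.1823 × 0.977 ÷ 0.2802 = 0.636 on the natural-log scale, or 0.276 on log10.

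Simulating the rank-sum at that SD gives 79.4% (10,000 runs). The stated 80% is therefore a figure for the unadjusted test, and it depends on an SD of about 0.636. At SD 1.0, simulated power is 42%.

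**2. Leaving out the stratum.** Let R² be the share of log fold-rise variance explained by the two-level stratum (assumed; strata 50/50; total SD held at 0.636). With balanced strata the approximate true type I error is 2 × [1 − Φ(1.96/√(1 − R²))]. For example, R² = 0.20 gives 1.96/√0.80 = 2.191, hence 0.028. Simulation (5,000 runs per cell, power at ratio 1.2):

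| R² | Rank-sum type I error | Power: rank-sum / van Elteren / linear model |
|---|---|---|
| 0 | 0.052 | 80 / 79 / 81% |
| 0.05 | 0.045 | 81 / 82 / 84% |
| 0.10 | 0.037 | 80 / 83 / 85% |
| 0.20 | 0.029 | 83 / 88 / 90% |
| 0.30 | 0.020 | 83 / 92 / 92% |

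The rank-sum row never falls below the stated 80%. What is given up is the gain. At R² = 0.20, 400 × (1 − 0.20) = 320 adjusted patients carry the information of 400 unadjusted.

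**3. Leaving out baseline as a continuous covariate.** Assumptions: 400 patients; log10 baseline SD 1, limited to 2500 U/mL; floor 10 U/mL; residual SD 0.45 log10; true ratio 1.3. *Slope* is the change in log10 fold-rise per 1 log10 of baseline; a slope of 0 means fold-rise does not depend on baseline.

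| Slope | Rank-sum type I error | Power: rank-sum / van Elteren / ANCOVA |
|---|---|---|
| 0 | about 5% | about 70 / 70 / 71% |
| −0.2 | 4–5% | about 66 / 68 / 72% |
| −0.35 | about 3% | about 58 / 65 / 70% |
| −0.5 | about 1.8% | about 49 / 63 / 71% |

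With 2,000 to 3,000 runs per cell, the Monte Carlo standard error is roughly 1 point for power (√(0.7 × 0.3/3000) = 0.8 points). Repeats with minor differences in set-up move the figures by a few points; the −0.5 row ranges over 45–50 / 57–64 / 67–72%. The assumed SD of 0.45 exceeds the 0.276 implied in step 1, so compare methods within a row, not any entry with 80%.

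**4. Why the stratum may not be enough.** The upper stratum now runs from 50 to 2500 U/mL, log10(2500/50) = 1.70 log units. Under the earlier 250 ceiling it was log10(250/50) = 0.70. At an assumed slope of −0.35, expected fold-rise would differ by 10^(0.35 × 1.70) = 3.9-fold across that stratum. This is why ANCOVA gains over van Elteren in the lower rows.

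**5. What the documents say about the slope.** Section 1.3 reports that among low positives "seroconversion rates above threshold were 80-100% and to a level approximately 5-fold higher than that observed in seronegative participants", against 27–44% seroconversion in negatives. That describes post-dose level, not fold-rise. A low positive starting at 50 and a negative floored at 10 differ 50/10 = 5-fold at baseline. If they also end 5-fold apart, their fold-rises are equal. The background is thus compatible with slope 0 and does not fix another value.

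**The case against.** The best defence is that nothing here invalidates the trial. With participants randomised individually, the rank-sum keeps its error at or below 5%. Section 13.7 computed power for this same test. A rank test also copes well with values piled up at the 10 U/mL floor. All of that stands.

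Several stronger readings are tempting, and the documents do not support them:

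- *The test is conservative and loses power.* Only if titre predicts fold-rise. At slope 0 the methods are equal.
- *Baseline titre is ignored.* It is the endpoint's denominator; only dependence beyond that is unadjusted.
- *The trial falls short of 80% because of this choice.* The 80% was computed for the unadjusted test. The unstated SD is the larger uncertainty about power.
- *Omitting regimen makes the test conservative, or the pooled arm is diluted by a known amount.* Regimen is not a randomisation factor. Leaving it out may cost precision but does not produce this conservatism. The documents give neither the regimen mix nor effects by regimen. A pooled comparison of the reduction strategy is a legitimate target.
- *Whole sites are randomised.* Section 13.3 can be read so, and an unadjusted test would then be anti-conservative. Appendix 1 points to individual randomisation, so this looks like a wording fault.

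The objection does not touch the missing stratum or the missing estimate and interval.

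**Conclusion.** The point holds as a worthwhile, nearly free improvement, not as a validity fault. Three facts need no assumptions: the primary test omits the titre stratum, it does not adjust for baseline beyond division, and no effect size or interval is planned for the primary endpoint. The size of the efficiency loss is conditional. Under the inputs in step 3, ANCOVA gains about 1 power point at slope 0 and about 6, 12 and 22 points at slopes −0.2, −0.35 and −0.5. The rank-sum's type I error falls from about 5% to about 1.8% over that range. The slope, baseline distribution and residual SD are all assumed, and no document figure selects among the rows. Adjustment costs essentially nothing if baseline is uninformative.

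**What to change.** 1. Replace the primary test with one of these:
   - a van Elteren test stratified by the randomisation titre stratum, with a Hodges-Lehmann ratio of fold increase and 95% CI; or
   - a linear model of log10 Day 30 titre on arm, log10 baseline titre and titre stratum, reporting the geometric mean ratio with 95% CI. Keep the stratified rank test as a sensitivity analysis because of the 10 U/mL floor.
2. Report the ratio and CI by baseline regimen (MMF withheld or CNI reduced, each against controls on the same regimen) as a secondary estimate.
3. If participants are individually randomised, as Appendix 1 indicates, describe randomisation in section 13.3 as stratified (blocked) by site instead of clustered.
4. Name the pre-dose Roche result that serves as denominator and covariate. The Roche rows in Appendices 2 and 3 start at Week 2.

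**Cost.** Wording and programming only; no additional patients. The trial is open-label and under way (section 6 refers to protocol v8.0 and beyond), and the DSMB may see antibody results by arm (13.5.1). Blinding therefore cannot protect the timing of the change. Make it by a dated amendment before any comparison of antibody results by arm, decided by people without access to such results. Report the currently planned rank-sum as a sensitivity analysis. The linear model adds a log-scale assumption, which the stratified rank test checks.

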13.4.3 Analyses of Secondary and Other Endpoint(s)/Outcome(s)

All binary secondary endpoints will be analyzed using a Fisher exact test. Severe adverse events will be analyzed by calculating the incidence rate difference with a two-sided 95% confidence interval for immunoreduction vs no immunoreduction participants.

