Principal Investigator	The physician responsible for supervising the conduct of the clinical investigation and for protecting the rights, safety, and welfare of participants consistent with 21 CFR Part 312.
Participant Premature Termination	Participants who are lost to follow up, withdraw consent, or die during the study. Data and specimens will no longer be expected from participants who are terminated from the study.
Program Officer	NIAID official who oversees the programmatic and budgetary aspects of the grant.
Protocol Mandated Procedures	A procedure or intervention that is a study requirement at the specified time point in the protocol.
Regulatory Affairs Officer	NIAID-assigned officer responsible for regulatory aspects of the study.
Site Principal Investigator	Lead investigator listed on the Investigator of Record Agreement at a particular clinical site who is responsible for the conduct of the study at that site.
Investigational Product	The investigational product is an additional dose of the Moderna or Pfizer-BioNTech COVID-19 vaccine
Immunosuppression Reduction	Protocol-mandated reduction in immunosuppression, determined by the participant's baseline regimen. See Section 6.3 .

1. Background and Rationale

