2.4 Secondary Efficacy Objectives

To determine the incidence of symptomatic or asymptomatic SARS-CoV-2 infection in the 12 months following the additional dose of vaccine.

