8.3.3 Follow-up Visits (All Participants)

Follow-up will occur at weeks 1, 2, 3, 4, 5, 6 and Months 3, 6, 9, and 12 following vaccine administration. Participants will have additional blood tests to monitor their graft function during the time they are on a reduced level of immunosuppression and for 1 month following resumption of their original regimen of immunosuppression. Identical blood testing schedules will take place for both the COVID-19 vaccine dose group and the IS reduction plus COVID-19 vaccine dose group. Kidney recipients will have their serum creatinine levels measured at the weekly visits. Liver recipients will have a hepatic panel (AST, ALT, alk phos, bilirubin, direct bilirubin) at the weekly visits.

The Week 4 visit is the primary endpoint visit. During these visits, participants will be asked about their general health, any new events, immunosuppression medications and their transplanted organ per the Schedule of Events in Appendix 2.

Blood and nasal swabs will be collected for assessments to be run in the clinical and research laboratories per the Schedule of Events in Appendix 2 or Appendix 3 based on group assignment. Nasal mid-turbinate swabs for SARS-CoV-2 PCR testing will be collected at baseline and Months 1, 3, 6, 9 and 12 following vaccine administration.

Participants will be instructed to contact the study team if they receive any COVID-19 testing at an outside lab during the course of the study. All instances of COVID-19 infection will be reported on the applicable electronic case report form.

A subset of participants will have a study visit on Day 3 to have blood drawn for a research laboratory study to detect the presence of SARS-CoV-2 spike protein generated in response to the vaccine.

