11.1 Participant Completion

All participants will be followed for 12 months following the COVID-19 vaccine administration.

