11.3 Participant Replacement

Participants who withdraw or are withdrawn will not be replaced.

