Appendix 2: Schedule of Events (COVID-19 Vaccine Dose Alone)

Study Schedule	Days		Weeks						Months				
Time points	0	3 ¹	1	2	3	4	5	6	3	6	9	12	For Cause ²
Visit #	01	02	03	04	05	06	07	08	09	10	11	12	FC
Visit Windows (+/-)	-	1d	1d	3d	3d	3d	3d	3d	2w	2w	2w	2w	-
General Assessments													
Study Contact ³	X		X	X	X	X	X	X	X	X		X	X
Medications (immunosuppression, PrEP, COVID-19 treatment)	X ⁴	→	→	→	→	→	→	→	X	X ⁵	X ⁵	X ⁵	X
Assessment of Events (AE, SAE, rejection, graft loss)	X	→	→	→	→	→	→	→	→	→	→	X	X
Clinical Laboratory Assessments													
Complete Blood Count with differential	X			X		X			X	X		X	
Metabolic Panel ⁶	X								X	X		X	
eGFR, serum creatinine (kidney)	X		X	X	X	X	X	X					
Hepatic Panel including direct bilirubin (liver)	X									X			
Quantitative Immunoglobulins	X									X			
SARS-CoV-2 PCR (nasal swab, clinical)	X ⁷					X			X	X	X	X	X
Investigational Intervention													
COVID-19 mRNA Vaccine	X												
Central Laboratory Assessments													
SARS-CoV-2 PCR (nasal swab, research)	X					X			X	X		X	X
Oral fluid anti-N and anti-S immunoglobulin levels	X					X			X	X		X	X
Anti-SARS-CoV-2 S (Roche Elecsys®)				X		X			X	X		X	X
Donor Specific Antibodies (kidney only)						X			X	X		X	X
Antibody/Neutralization assays	X			X		X			X	X		X	X
Spike Protein (subset of sites)	X	X											
Proteomics	X	X ⁸				X							
Transcriptomics	X	X ⁷				X							
T and B Cell Assays	X			X		X			X	X		X	X

¹ May be a home draw. The spike protein will only be performed at a subset of clinical sites.

² Unscheduled "for cause" visit for suspected rejection. Participants with confirmed COVID-19 will send in a nasal swab for research.

³ Study contacts may be remote.

⁴ Ensure the participant has not taken any medications since screening that would make them ineligible.

⁵ Only PrEP and COVID-19 related treatment collected at these visits.

⁶ Comprehensive metabolic panel at baseline, basic metabolic panel all other timepoints (see study definitions).

⁷ If the Day 0 nasal swab is positive, the participant will be prematurely discontinued and followed until Day 30 for safety. This includes the Day 30 clinical labs, DSA and AE/SAE assessment. No further mechanistic blood will be collected.

⁸ These Day 3 assessments will only be collected on participants included in the Day 3 spike protein.

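### The 12-month COVID-19 endpoints are compared by Fisher's exact test without regard to length of follow-up, so the result depends on how early leavers are counted

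*Combined protocol and SAP*

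**What the plan says.** The objective in Section 2.4 is "To determine the incidence of symptomatic or asymptomatic SARS-CoV-2 infection in the 12 months following the additional dose of vaccine". Sections 3.3.2 and 13.2 list PCR positivity, symptomatic COVID-19 and COVID-19 hospitalisation as secondary efficacy endpoints and give them no time window of their own.

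Section 13.4.3 sets the test: "All binary secondary endpoints will be analyzed using a Fisher exact test". Section 13.4.1 sets the population: "the analysis population will consist of all individuals with a measurement for that outcome, in an intent-to-treat framework". The plan has no censoring, person-time or time-to-event rule for these endpoints, although Section 13.4.3 plans an incidence rate difference for severe adverse events.

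On follow-up, Section 11.1 says "All participants will be followed for 12 months following the COVID-19 vaccine administration". It can still end early:

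- Section 11.2 lists withdrawal of consent, loss to follow-up, death and investigator decision, and Section 11.3 adds "Participants who withdraw or are withdrawn will not be replaced".
- The Study Definitions page says of terminated participants: "Data and specimens will no longer be expected from participants who are terminated from the study".
- For a positive Day 0 swab, footnote 7 of Appendix 2 says "the participant will be prematurely discontinued and followed until Day 30 for safety". Appendix 3 also ends follow-up at Day 30 in that case.

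On data capture, Section 8.3.3 says "All instances of COVID-19 infection will be reported on the applicable electronic case report form". It schedules PCR swabs at baseline and Months 1, 3, 6, 9 and 12.

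**The concern.** A yes/no outcome over 12 months is fully known only for someone who has the event or is observed for the whole year. A person who leaves uninfected at month 4 has neither. The population rule can then be read in three ways: count that person as infection-free, drop them while keeping leavers who were infected first, or restrict to people who complete the year. The plan does not choose, and Fisher's test on the resulting table uses no follow-up time.

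Two things are at stake. The estimate of the Section 2.4 incidence depends on the reading. So does the comparison between arms if dropout differs by arm, which is plausible because Section 13.3 leaves participants and clinical staff unmasked. These are the trial's only clinical efficacy comparisons. The primary antibody endpoint is not affected.

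**Working it through.** **Inputs.** From Section 13.7: 200 per arm and α = 0.05. The plan states no infection rate, dropout rate or power for these endpoints, so there is no figure to reproduce. Assumed: constant hazards, dropout independent of infection, two-sided tests, and the risks and dropout rates shown below.

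**Step 1: crude proportion.** For 12-month risk p and dropout d, let λ = −ln(1−p) and μ = −ln(1−d).

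- Observed event proportion: e = λ/(λ+μ) × [1 − exp(−(λ+μ))].
- Proportion staying event-free to month 12: s = exp(−(λ+μ)) = (1−p)(1−d).
- Leavers counted infection-free: the estimate is e.
- Uninfected leavers excluded: the estimate is e/(e+s).
- Completers only: the estimate is p, because dropout is independent of infection.

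With p = 0.20 (λ = 0.2231):

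- d = 0.10: μ = 0.1054, s = 0.72, e = 0.679 × 0.28 = 0.190; excluded, 0.190/0.910 = 0.209.
- d = 0.20: μ = 0.2231, s = 0.64, e = 0.5 × 0.36 = 0.180; excluded, 0.180/0.820 = 0.220.
- d = 0.25: μ = 0.2877, s = 0.60, e = 0.437 × 0.40 = 0.175; excluded, 0.175/0.775 = 0.226.

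At equal dropout of 10-20% the error is therefore about 1-2 percentage points, downward or upward by rule. In simulation, Kaplan-Meier recovers 0.20 throughout.

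**Step 2: power at equal dropout** (2,000 simulated trials per row, simulation error about 1 point; HR is the hazard ratio):

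| Control risk, HR, dropout | Fisher, leavers infection-free | Fisher, leavers excluded | Fisher, completers | Chi-square, leavers infection-free | Log-rank |
|---|---|---|---|---|---|
| 20%, 0.5, 10% | 69.4 | 70.9 | 69.0 | 73.7 | 74.0 |
| 20%, 0.5, 20% | 63.6 | 65.2 | 62.0 | 69.0 | 69.5 |
| 30%, 0.6, 10% | 63.0 | 65.1 | 62.6 | 67.4 | 67.6 |
| 30%, 0.6, 20% | 61.9 | 62.6 | 58.4 | 66.1 | 66.8 |

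Under the first two rules, in most settings, Fisher gives up about 3-6 points to log-rank. Across control risks of 10-40% the full range is 2.5-7.8 points; completers-only loses up to 8.8. Uncorrected chi-square uses the same yes/no data without dates and stays within 1.5 points of log-rank across those risks. Most of the loss is therefore the exact test's conservatism.

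**Step 3: dropout of 10% v 25%.**

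- No true effect, 20% risk: from Step 1, counting leavers as infection-free gives 0.190 v 0.175, and excluding them gives 0.209 v 0.226. The spurious differences are 1.5 and 1.7 points, in opposite directions.
- No true effect, 30% risk: Fisher's type I error is about 6-6.5%, against about 5% for log-rank. A smaller 2,000-trial run gave 5.7% and 7.0% under the two rules.
- Control risk 20%, HR 0.5, heavier dropout in the lower-risk arm: Fisher's power is about 76-78% with leavers counted infection-free and 55% with them excluded, against about 69-71% for log-rank. With the heavier dropout in the other arm the order reverses: 53% and 79%, against 71%.

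**Step 4: dropout of 5% v 15%.** At 30% risk in both arms, the formulas give 0.293 v 0.278 (leavers infection-free) and 0.306 v 0.319 (leavers excluded), spurious differences of 1.5 and 1.3 points. The standard error of a difference is √(2 × 0.3 × 0.7/200) = 4.6 points. Fisher's simulated error is 4.8% and 5.2%, which is nominal.

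**The case against.** The case for leaving the plan alone is fair. These are secondary endpoints with no planned power, everyone is due the same 12 months, and Fisher's test is a valid if conservative choice. A completers-only reading of the population rule is open, and it is nearly unbiased when dropout is non-informative.

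Four stronger readings are tempting, and the documents do not support them:

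- **That follow-up is staggered by design.** It is not. Section 11.1 fixes 12 months, and inequality comes only from early departure and the Day 0 PCR rule.
- **That the 12-month incidence will be biased.** Bias needs dropout, for which no rate is stated, and it depends on a rule that is not written. Its sign can go either way.
- **That power is lost because infection dates are discarded.** Step 2 shows otherwise. Dates add noticeably (2.5-3 points over chi-square) only at about 50% risk.
- **That Fisher's test inflates false positives in general.** At equal dropout it is conservative, and at 5% v 15% it is nominal. Inflation appears only with a wider imbalance.

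One practical objection stands in full. Infections found only by scheduled swab have no exact date, so an ordinary log-rank test fits PCR positivity poorly.

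What the objection does not answer is that the choice between readings is unwritten. With unequal dropout, that choice can move power by more than 20 points.

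**Conclusion.** The concern holds in a limited form. As written, the Section 2.4 incidence is to be estimated without using follow-up time, and the estimate depends on how early leavers are counted. The consequence is small if dropout is low or balanced: about 1-2 percentage points at 20% risk, plus about 3-6 points of power that Fisher's conservatism costs in any case. It becomes material if dropout differs widely by arm: at 10% v 25%, power is about 55-78% by counting rule, and type I error at 30% risk is about 6-6.5%.

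All sizes rest on assumed infection and dropout rates, constant hazards and dropout unrelated to infection. If people leave for reasons linked to infection risk, a censored analysis is biased too. The simulations used exact event times and an unstratified log-rank test, so they indicate the gain but do not measure it for the stratified or interval-censored versions proposed below. The change is worth making before the data are analysed; it does not bear on the primary conclusion.

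**What to change.** In Section 13.4.3:

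- **Symptomatic COVID-19 and COVID-19 hospitalisation.** Analyse time from the study vaccine dose (Day 0, matching Section 2.4) to first event through 12 months, censored at last contact. Report cumulative incidence by arm with death as a competing event, a 95% CI for the difference, and a two-sided log-rank test stratified by pre-dose titre (<50 v ≥50 U/mL, the Section 13.3 factor).
- **PCR positivity.** Use a visit-based (discrete-time) or interval-censored version of the same analysis. Section 8.3.2 places the Day 0 samples before vaccination, so do not count Day 0 positives as outcome events.
- **Fisher's test.** Keep it for the 30-, 60- and 90-day safety endpoints.

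The cost is a few lines of SAP text and reliance on an infection date from the eCRF; the documents do not describe the date fields, so confirm that one is collected. Swab-only infections will be dated coarsely, to the interval between scheduled visits.
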